Drug-drug interaction recommendations provided for acalabrutinib in this protocol are made with respect to the presence of life-threatening COVID-19 infection and ability to achieve pharmacodynamic (PD) Btk receptor occupancy steady-state in target B-cell and monocytic populations. Therefore, the Sponsor recommends that all eligible subjects with COVID-19 begin dosing with acalabrutinib 100 mg bid. The duration of acalabrutinib therapy will be limited to 10 days (a maximum of 20 doses). Table 4 provides moderate CYP3A inhibitors and acid reducing agent guidance for subjects with COVID-19. Refer to Appendix E for a list of common CYP3A inhibitors/inducers and gastric acid reducing medicines.

Table 4	Acalabrutinib Use with Moderate CYP3A Inhibitors and Gastric Acid
	Reducing Agents

	Co-administered Medicines	Recommended Acalabrutinib Use
CYP3A Inhibitor	Moderate CYP3A inhibitor	Monitor subjects closely for adverse reactions if taking moderate CYP3A inhibitors. For subjects who experience an intolerable adverse event (ie, Grade 3-4) attributed to acalabrutinib therapy, reduce the dose to 100 mg once daily.
Gastric Acid Reducing Medicines	Proton-pump inhibitors (PPIs)	Avoid concomitant use. If PPI concomitant use cannot be avoided, dose modification of acalabrutinib is not necessary; however, acalabrutinib must be administered with at least 100 mL of COCA-COLA to improve acalabrutinib absorption (refer to Section 6.1.3.1). Other cola beverages are not permitted.
	H2-receptor antagonists	Take acalabrutinib 2 hours before taking a H2-receptor antagonist.
	Antacids	Separate dosing by at least 2 hours.

6.5.4.1 Active Substances That May Increase Acalabrutinib Plasma Concentrations CYP3A Inhibitors

Co-administration with a strong CYP3A inhibitor (200 mg itraconazole qd for 5 days) increased acalabrutinib maximum observed concentration (C_{max}) and area under the concentration-time curve (AUC) by 3.7- and 5.1-fold in healthy subjects (N=17), respectively.

Consider alternative therapies that do not strongly inhibit CYP3A activity. In subjects requiring strong CYP3A inhibitors (eg, ketoconazole, conivaptan, clarithromycin, indinavir, itraconazole, ritonavir, telaprevir, posaconazole, voriconazole), discontinue acalabrutinib treatment.

6.5.4.2 Active Substances That May Decrease Acalabrutinib Plasma Concentrations CYP3A Inducers

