6.6.1 Hemorrhage

Bleeding events, some fatal, including central nervous system, respiratory, and gastrointestinal hemorrhage, have been reported in subjects treated with acalabrutinib.

Please refer to Section 6.7 for study drug modification guidance.

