6.7 Dose Modification and Toxicity Management

In general, no acalabrutinib dose modification is required if a subject experiences a Grade 1 or Grade 2 AE. Acalabrutinib therapy should be modified or discontinued, however, for the following AEs:

Event	Acalabrutinib Dose Modification/Discontinuation	
Hematological		
Grade 4 neutrophil count decrease (ANC < 500/μL)	 Hold acalabrutinib, and consider introducing growth factors (eg, G-CSF) and continue to monitor ANC If neutropenia has improved to Grade 1 or baseline within 3 days of event onset, restart acalabrutinib If neutropenia has not improved to Grade 1 or baseline within 3 days of event onset, discontinue acalabrutinib 	
Any grade febrile neutropenia lasting more than 2 days	 Discontinue acalabrutinib Consider introducing growth factors (eg, G-CSF), evaluate subject for infection, and begin antibiotic treatment per institutional guidelines 	
 Presence of significant bleeding events with or without thrombocytopenia, such as: Grade 3 or 4 hemorrhage Any grade serious hemorrhage event Any grade intracranial hemorrhage or hematoma 	Discontinue acalabrutinib	
Grade 4 platelet count decrease (< 25,000/mm3)	 Hold acalabrutinib and consider platelet transfusions, as clinically indicated If thrombocytopenia has improved to ≤Grade 2 within 3 days of event onset, restart acalabrutinib If thrombocytopenia has not improved to ≤Grade 2 within 3 days of event onset, discontinue acalabrutinib 	
Gastrointestinal/hepatic		
Grade 3 or 4 nausea, vomiting, or diarrhea, if persistent despite optimal antiemetic and/or antidiarrheal therapy	Discontinue acalabrutinib	

Event	Acalabrutinib Dose Modification/Discontinuation
Acute hepatic toxicity or hepatic failure, which is of such severity that after evaluation by a hepatologist, would consider appropriate to stop all non- essential medications	Discontinue acalabrutinib
Cardiovascular	
Grade 3 or 4 hypertension, if persistent despite optimal antihypertensive therapy	Discontinue acalabrutinib
Grade 3 or 4 arrhythmias that are sustained or associated with cardiovascular instability	Discontinue acalabrutinib
Infections	
Severe opportunistic infection (such as Pneumocystis jirovecii pneumonia, toxoplasmosis, disseminated Mycobacterium avium complex, PML)	Discontinue acalabrutinib
Grade 3 confirmed bacterial infections	 Hold acalabrutinib If infection does not respond to appropriate antimicrobial therapy within 48-72 hours, discontinue acalabrutinib

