Grade 4 confirmed bacterial infections	Discontinue acalabrutinib
Other	
Any non-COVID-19-related Grade 4 AE	Discontinue acalabrutinib
Any other Grade 3 or Grade 4 toxicity that persists despite optimal medical management	Discontinue acalabrutinib

AE = adverse event; ALT = alanine aminotransferase; ANC = absolute neutrophil count; ALP = alkaline phosphatase; AST = aspartate aminotransferase; G-CSF = granulocyte colony-stimulating factor; PML = progressive multifocal leukoencephalopathy.

Clinical judgment should be used to determine appropriate management of the subject during any AE.

Acalabrutinib may be held for a maximum of 3 consecutive days (6 consecutive doses) from expected dose due to toxicity. Any other clinically important events where dose delays may be considered appropriate by the Investigator, as well as continuation of therapy after a dose is held beyond 3 days, must be discussed with the Medical Monitor. If a dose is missed due to an AE or for any other reason, missed doses should be completed so the subject receives a maximum of 20 doses of study drug, even if this is beyond the 10-day dosing period.

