6.7.2 Hepatic Impairment

Acalabrutinib clinical safety has not been evaluated in patients with severe hepatic impairment. If acalabrutinib is administered to subjects with hepatic impairment, monitor subjects carefully for AEs and follow recommendation dose modifications in Section 6.7.

The PK acalabrutinib in subjects with hepatic impairment has been studied. Briefly, the AUC of acalabrutinib increased 1.9-fold in subjects with mild hepatic impairment (Child-Pugh class A), 1.5-fold in subjects with moderate hepatic impairment (Child-Pugh class B) and 5.3-fold in subjects with severe hepatic impairment (Child-Pugh class C) compared with subjects with normal liver function. No clinically relevant PK difference in ACP-5862 was observed in subjects with severe hepatic impairment (Child-Pugh class C) compared with subjects with normal liver function. No clinically relevant PK differences in acalabrutinib and ACP-5862 were observed in subjects with mild or moderate hepatic impairment (total bilirubin less and equal to ULN and AST greater than ULN, or total bilirubin greater than ULN and any AST) relative to subjects with normal hepatic function (total bilirubin and AST within ULN).

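### For subjects on a moderate CYP3A inhibitor, Table 4 says to reduce the dose for an attributed Grade 3-4 event where Section 6.7 says to discontinue for some of the same events, and no text ranks the two rules

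*Protocol*

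**What the plan says.** Protocol 6.1.3.1 sends sites to Section 6.5.4 for dosing with interacting drugs, including moderate CYP3A inhibitors. In Table 4 of that section, the moderate-inhibitor row asks for close monitoring and then gives one action: "For subjects who experience an intolerable adverse event (ie, Grade 3-4) attributed to acalabrutinib therapy, reduce the dose to 100 mg once daily". The wording in brackets equates intolerable with Grade 3-4.

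Protocol 6.7 is the general toxicity table for acalabrutinib. Its action is to discontinue for each of these events:

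- "Grade 3 or 4 hemorrhage"
- "Grade 3 or 4 arrhythmias that are sustained or associated with cardiovascular instability"
- "Grade 4 confirmed bacterial infections"
- "Any non-COVID-19-related Grade 4 AE"

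Section 6.7 does not mention CYP3A inhibitors or Table 4, and Table 4 does not mention Section 6.7.

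Elsewhere, Section 6.6.1 on hemorrhage says: "Please refer to Section 6.7 for study drug modification guidance". For hepatic impairment, another setting discussed for raised exposure, Section 6.7.2 says to "monitor subjects carefully for AEs and follow recommendation dose modifications in Section 6.7".

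**The concern.** A site with a subject on, say, fluconazole, ciprofloxacin or verapamil (all listed as moderate inhibitors in Appendix E) who has a Grade 3-4 bleed attributed to acalabrutinib has a valid route to two instructions. Followed literally, Table 4 keeps that subject on acalabrutinib once daily, while 6.7 stops it. This is first a matter of individual patient safety.

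It also touches the safety counts. Adverse events leading to discontinuation are part of the primary safety endpoint (Protocol 3). The discontinuation rate for attributed toxicity feeds an enrollment-pause criterion in Protocol 4.4: 20% or more once at least 10 acalabrutinib subjects have been treated, which is 2 subjects at exactly 10. A case handled by reduction rather than discontinuation would drop out of both counts. No efficacy estimate, power figure or error rate depends on it.

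**Working it through.** The plan states no figure to reproduce here, so the check sets the two rules side by side.

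**1. Scope.** Table 4 applies when three conditions hold: a moderate CYP3A inhibitor, Grade 3-4, and attribution to acalabrutinib. Section 6.7 applies to acalabrutinib treatment generally, and most of its rows need no attribution. The overlap is therefore attributed Grade 3-4 events in moderate-inhibitor users.

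**2. The 13 rows of 6.7, sorted by how they meet Table 4.**

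| Type of row in 6.7 | Rows | Number | Compatible with reducing to once daily? |
|---|---|---|---|
| Discontinue; Grade 3 and/or 4 named; no persistence or response condition | Hemorrhage; sustained or unstable arrhythmia; Grade 4 bacterial infection; non-COVID-19 Grade 4 AE | 4 | No |
| Hold first | Grade 4 neutrophils; Grade 4 platelets; Grade 3 bacterial infection | 3 | Yes: hold, then restart once daily |
| Discontinue only if persistent | Nausea, vomiting or diarrhea; hypertension; any other Grade 3-4 toxicity | 3 | Yes: reduce, then stop if it persists |
| Discontinue; not defined by Grade 3-4 | Febrile neutropenia over 2 days; hepatic toxicity; severe opportunistic infection | 3 | Not counted; overlap depends on the case |

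Check: 4 + 3 + 3 + 3 = 13. Rows offering a dose reduction: 0.

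**3. How firm the four are.** Three are clear. The fourth depends on reading. Taken literally, the Grade 4 row also collides with 6.7's own hold rows for Grade 4 neutrophils and platelets, so it is read here as covering Grade 4 events that have no row of their own.

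**4. Restart dose.** Two of the three hold rows provide for a restart but state no dose, for example "If neutropenia has improved to Grade 1 or baseline within 3 days of event onset, restart acalabrutinib". The Grade 3 bacterial infection row gives no restart instruction. Table 4's once-daily dose therefore has a sensible role after a hold.

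**5. Search for a ranking.** None was found in either document. The rule that the specific overrides the general does not decide it, because 6.7 is specific by event and Table 4 by population.

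**6. Whether dosing was still under way.** The SAP amendment history records on 08 September 2020 that the total randomized was known, and SAP 1.3 says recruitment was complete at 62. The last dated SAP change is 30 September 2020, which is 22 days later. Twenty doses twice daily take 10 days; one maximum 3-day hold makes about 13, and 13 < 22. Dosing was very probably over, though doses missed for other reasons may also be made up later.

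**The case against.** The best reply is that the protocol already assigns these events to 6.7. That section is the one titled for dose modification and toxicity management. The risk sections on hemorrhage, infections, cytopenias and atrial fibrillation all point to it, with no exception for CYP3A inhibitor users. Table 4 is interaction guidance and frames its entries as recommended use. Section 6.7 adds that clinical judgment should guide management of any adverse event, Section 8 takes immediate safety concerns to the Medical Monitor to decide on continuing, and Section 4.4 pauses enrollment for any attributed Grade 4 hemorrhage. A site is unlikely to leave a bleeding subject on the drug unnoticed.

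Most of this stands. It shows probable intent and lowers the risk, and it is why the point is minor. It does not supply a ranking. The arrhythmia pointer covers only atrial fibrillation and flutter. The judgment sentence and the Medical Monitor route are ways to escalate a question and do not answer it. The pause governs enrollment of further subjects, not dosing of the one who bled. Section 6.1.3.1 points the other way, to 6.5.4. Section 6.7.2 shows that the authors could write the missing cross-reference when they meant it.

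**Conclusion.** The two instructions conflict for four rows of 6.7, three of them without any interpretation, and no text says which prevails. The surrounding text suggests that 6.7 was intended. Severity is minor: a correction to safety wording, with no effect on efficacy.

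Three stronger readings do not hold:

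- A reader might infer that the protocol requires bleeding subjects to stay on acalabrutinib, or that some did. The documents show only that one rule, taken alone, would allow it. They report no cases.
- A reader might infer that the whole of 6.7 contradicts Table 4. The hold rows and the persistence rows can be reconciled with it, and the three rows not defined by Grade 3-4 are not counted.
- A reader might try to turn Table 5 into an expected number of bleeds. Its Grade 3 or higher hemorrhages (28 of 1040) come from long-term dosing in hematologic malignancy. The 9.8-month median onset belongs to the 37 major hemorrhages of any grade, not to those 28. Nothing supports spreading events evenly over time, and the documents give neither the rate of moderate-inhibitor use nor a bleeding rate in COVID-19.

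That very few subjects are affected is therefore a judgment, resting on 30 planned acalabrutinib subjects, a course of at most 20 doses, and the need for inhibitor use, an attributed Grade 3-4 event and one of four event types to coincide.

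**What to change.** Add one sentence to the moderate CYP3A inhibitor row of Table 4: *Section 6.7 hold and discontinuation rules take precedence; the reduction to 100 mg once daily applies only where Section 6.7 allows treatment to continue or restart.* This also supplies the dose on restart that 6.7 leaves open. The sponsor's clinicians should confirm that once-daily restart is intended, since 6.7 itself is silent on it.

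If dosing is complete, the wording matters only where the text is reused. The practical step is then to match two listings already planned, adverse events with grade, relationship and action taken (SAP 4.4.1) and concomitant treatments (SAP 4.2.4). Report in the clinical study report any acalabrutinib-treated subject with an attributed Grade 3-4 event while on a moderate CYP3A inhibitor, with the action taken and whether 6.7 called for discontinuation. A finding of no such subject closes the point. The cost is one sentence or one cross-check, with no new data and no change to any planned analysis.

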6.6 Risks Associated with Acalabrutinib

The safety profile of acalabrutinib in patients with COVID-19 is not yet established. The COVID-19 population is distinct from patients with hematologic malignancies, the population for which acalabrutinib is indicated, and the duration of acalabrutinib treatment for COVID-19 is much shorter than for the indicated population with hematologic malignancies. Therefore,

the safety profile of acalabrutinib in the COVID-19 population may differ from that established in the cancer population.

The experience with chronic administration of acalabrutinib in hematologic cancer studies is described below. Table 5 summarizes the risks associated with acalabrutinib (any grade, \geq Grade 3, and mean time to first onset) based on 1040 subjects with hematologic malignancies who received acalabrutinib monotherapy (data on file).

For more detailed information on treatment-emergent adverse events (TEAEs), refer to the acalabrutinib Investigator's Brochure. Full details regarding the clinical safety of acalabrutinib are presented in Sections 5 and 6 of the acalabrutinib Investigator's Brochure.

Event esterory	Number (%) of subjects		Median (min, max), months	
Event category	Any grade	≥Grade 3	Time to first onset	
Hemorrhage	482 (46.3)	28 (2.7)	1.2 (0, 53)	
Major hemorrhage	37 (3.6)	28 (2.7)	9.8 (0, 44)	
Infections	694 (66.7)	183 (17.6)	3.2 (0, 45)	
Anemia	144 (13.8)	81 (7.8)	0.7 (0, 41)	
Neutropenia	163 (15.7)	148 (14.2)	3.1 (0, 44)	
Thrombocytopenia	93 (8.9)	50 (4.8)	1.7 (0, 39)	
Second primary malignancy	127 (12.2)	43 (4.1)	9.5 (0, 50)	
Atrial fibrillation	46 (4.4)	13 (1.3)	17.4 (0, 43)	

Table 5Risks Associated with Acalabrutinib Monotherapy in Subjects With
Hematologic Malignancies (N = 1040)

max = maximum; min = minimum.

6.6.1 Hemorrhage

Bleeding events, some fatal, including central nervous system, respiratory, and gastrointestinal hemorrhage, have been reported in subjects treated with acalabrutinib.

Please refer to Section 6.7 for study drug modification guidance.

6.6.2 Infections

Serious infections, including fatal events, have been reported in subjects treated with acalabrutinib (eg, aspergillosis). Subjects should be monitored for signs and symptoms of infection and treated as medically appropriate. Please refer to Section 6.7 for study drug modification guidance.

6.6.3 Hepatitis B Reactivation

Across the acalabrutinib clinical development program, 9 subjects had hepatitis B virus (HBV) reactivation. Seven of the 9 subjects developed HBV reactivation after receiving acalabrutinib, and 2 subjects had HBV reactivation prior to receiving (crossover) acalabrutinib. One subject experienced a serious Grade 4 event that subsequently resulted in liver failure and death. Subjects who are anti-HBc positive or have a known history of HBV infection may be monitored monthly with a quantitative PCR test for HBV DNA, when clinically indicated. Any subject with a rising viral load (above lower limit of detection) should discontinue study treatment and have antiviral therapy instituted and a consultation with a physician with expertise in managing hepatitis B. Insufficient data exist regarding the safety of resuming acalabrutinib in subjects who develop HBV reactivation.

6.6.4 Progressive Multifocal Leukoencephalopathy

Across the acalabrutinib clinical development program, 2 subjects had events of PML (both serious) after receiving acalabrutinib. Signs and symptoms of PML may include cognitive and behavioral changes, language disturbances, visual disturbances, sensory deficits, weakness, and coordination and gait difficulties. Please refer to Section 6.7 for study drug modification guidance.

6.6.5 Cytopenias

Grade 3 or 4 events of cytopenias, including anemia, neutropenia, and thrombocytopenia have occurred in subjects treated with acalabrutinib. Monitor blood counts as specified in the SoA and as medically appropriate. Please refer to Section 6.7 for study drug modification guidance.

6.6.6 Second Primary Malignancies

Second primary malignancies, including non-skin carcinomas solid tumors and skin cancers, have been reported in subjects with B-cell malignancies treated with acalabrutinib. The most frequent second primary malignancy was skin cancer (squamous basal cell carcinoma of the skin). Subjects should be monitored for signs and symptoms of malignancy. Subjects who develop a malignancy should be managed according to institutional guidelines with diagnostic evaluations or as clinically indicated, and it may be necessary for subjects to permanently discontinue study treatment. Continuation of acalabrutinib treatment should be discussed with the Medical Monitor.

6.6.7 Atrial Fibrillation

Monitor for symptoms of atrial fibrillation and atrial flutter (eg, palpitations, dizziness, syncope, chest pain, dyspnea), and obtain an electrocardiogram (ECG) as clinically indicated. Subjects with atrial fibrillation should be managed per institutional guidelines with supportive care and diagnostic evaluations or as clinically indicated. Please refer to Section 6.7 for study drug modification guidance.

6.6.8 Reference Safety Information

See the Reference Safety Information in the acalabrutinib Investigator's Brochure for assessment of expectedness of serious adverse reactions.

6.7 Dose Modification and Toxicity Management

In general, no acalabrutinib dose modification is required if a subject experiences a Grade 1 or Grade 2 AE. Acalabrutinib therapy should be modified or discontinued, however, for the following AEs:

Event	Acalabrutinib Dose Modification/Discontinuation	
Hematological		
Grade 4 neutrophil count decrease (ANC < 500/μL)	 Hold acalabrutinib, and consider introducing growth factors (eg, G-CSF) and continue to monitor ANC If neutropenia has improved to Grade 1 or baseline within 3 days of event onset, restart acalabrutinib If neutropenia has not improved to Grade 1 or baseline within 3 days of event onset, discontinue acalabrutinib 	
Any grade febrile neutropenia lasting more than 2 days	 Discontinue acalabrutinib Consider introducing growth factors (eg, G-CSF), evaluate subject for infection, and begin antibiotic treatment per institutional guidelines 	
 Presence of significant bleeding events with or without thrombocytopenia, such as: Grade 3 or 4 hemorrhage Any grade serious hemorrhage event Any grade intracranial hemorrhage or hematoma 	Discontinue acalabrutinib	
Grade 4 platelet count decrease (< 25,000/mm3)	 Hold acalabrutinib and consider platelet transfusions, as clinically indicated If thrombocytopenia has improved to ≤Grade 2 within 3 days of event onset, restart acalabrutinib If thrombocytopenia has not improved to ≤Grade 2 within 3 days of event onset, discontinue acalabrutinib 	
Gastrointestinal/hepatic		
Grade 3 or 4 nausea, vomiting, or diarrhea, if persistent despite optimal antiemetic and/or antidiarrheal therapy	Discontinue acalabrutinib	

Event	Acalabrutinib Dose Modification/Discontinuation
Acute hepatic toxicity or hepatic failure, which is of such severity that after evaluation by a hepatologist, would consider appropriate to stop all non- essential medications	Discontinue acalabrutinib
Cardiovascular	
Grade 3 or 4 hypertension, if persistent despite optimal antihypertensive therapy	Discontinue acalabrutinib
Grade 3 or 4 arrhythmias that are sustained or associated with cardiovascular instability	Discontinue acalabrutinib
Infections	
Severe opportunistic infection (such as Pneumocystis jirovecii pneumonia, toxoplasmosis, disseminated Mycobacterium avium complex, PML)	Discontinue acalabrutinib
Grade 3 confirmed bacterial infections	 Hold acalabrutinib If infection does not respond to appropriate antimicrobial therapy within 48-72 hours, discontinue acalabrutinib
Grade 4 confirmed bacterial infections	Discontinue acalabrutinib
Other	
Any non-COVID-19-related Grade 4 AE	Discontinue acalabrutinib
Any other Grade 3 or Grade 4 toxicity that persists despite optimal medical management	Discontinue acalabrutinib

AE = adverse event; ALT = alanine aminotransferase; ANC = absolute neutrophil count; ALP = alkaline phosphatase; AST = aspartate aminotransferase; G-CSF = granulocyte colony-stimulating factor; PML = progressive multifocal leukoencephalopathy.

Clinical judgment should be used to determine appropriate management of the subject during any AE.

Acalabrutinib may be held for a maximum of 3 consecutive days (6 consecutive doses) from expected dose due to toxicity. Any other clinically important events where dose delays may be considered appropriate by the Investigator, as well as continuation of therapy after a dose is held beyond 3 days, must be discussed with the Medical Monitor. If a dose is missed due to an AE or for any other reason, missed doses should be completed so the subject receives a maximum of 20 doses of study drug, even if this is beyond the 10-day dosing period.

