4.4 Internal DMC

This study will have an iDMC. Details of the roles and responsibilities of the iDMC and the safety and efficacy review will be provided in a separate iDMC charter. The iDMC will be responsible for reviewing the safety data periodically.

The iDMC will review the cumulative safety data approximately 28 days after the first 30 subjects (approximately 15 subjects per arm) are randomized.

In addition, if at any time during the conduct of the study either of the criteria below are met, enrollment of additional subjects will be paused such that the iDMC would convene and conduct a full safety review.

- Any death due to acalabrutinib (per Investigator)
- ≥20% treatment discontinuation rate due to toxicity attributed to acalabrutinib (per Investigator), when 10 or more acalabrutinib subjects have been treated
- Any Grade 4 hemorrhage due to acalabrutinib (per Investigator)

During the safety review, the iDMC with compare the known adverse event (AE) profile associated with acalabrutinib with comprehensive safety data from the current study. The iDMC will determine if an unacceptable increase in Grade 3 or higher AEs known to be associated with acalabrutinib occurred in the study. After the review, the iDMC will make a recommendation regarding study continuation, hold, or termination.

At the time of the safety review the iDMC will also review all available efficacy data and will support any health authority interactions or internal discussions based on their review. The study team will remain blinded to the data that the iDMC will review.

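### Protocol Section 6.7 tells sites both to restart and to discontinue acalabrutinib after a recovered Grade 4 neutrophil or platelet decrease, and states no precedence

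*Protocol*

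**What the plan says.** All the conflicting rows sit in one table, in Protocol Section 6.7.

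- **Grade 4 neutrophil decrease:** hold, then "If neutropenia has improved to Grade 1 or baseline within 3 days of event onset, restart acalabrutinib". If not recovered in that time, discontinue.
- **Grade 4 platelet decrease:** hold, then "If thrombocytopenia has improved to ≤Grade 2 within 3 days of event onset, restart acalabrutinib". If not recovered in that time, discontinue.
- **Gastrointestinal, hypertension and arrhythmia rows:** discontinue, each with a condition. These read "Grade 3 or 4 nausea, vomiting, or diarrhea, if persistent despite optimal antiemetic and/or antidiarrheal therapy", "Grade 3 or 4 hypertension, if persistent despite optimal antihypertensive therapy" and "Grade 3 or 4 arrhythmias that are sustained or associated with cardiovascular instability".
- **First row under the Other heading:** discontinue for "Any non-COVID-19-related Grade 4 AE", with no recovery, persistence or stability condition.
- **Last row:** discontinue for "Any other Grade 3 or Grade 4 toxicity that persists despite optimal medical management".

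The text after the table calls for clinical judgment during any AE, caps toxicity holds at 3 consecutive days (6 doses), and has missed doses made up to the 20-dose maximum. It does not rank the rows.

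Two other parts of the plan count discontinuations. AEs leading to discontinuation of study treatment belong to the primary safety endpoint (Protocol Section 3). One of the three enrollment-pause criteria in Protocol Section 4.4, repeated in SAP Section 6, is "≥20% treatment discontinuation rate due to toxicity attributed to acalabrutinib (per Investigator), when 10 or more acalabrutinib subjects have been treated".

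**The concern.** A drug-related Grade 4 neutrophil or platelet decrease would normally be judged unrelated to COVID-19, so it falls under both its own row and the blanket Grade 4 row. If it recovers inside the 3-day limit, its own row says restart and the blanket row says discontinue. Two sites could treat identical events in opposite ways, and each could point to the protocol.

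Three things depend on the row followed:

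- **Treatment.** Cytopenias are among the acalabrutinib risks listed in Section 6.6.5, and the rows decide whether drug is resumed after them.
- **The primary safety endpoint.** The event counts as an AE leading to discontinuation at one site and as a temporary hold at another. Section 8.6.7 sharpens this: deterioration in a mandated laboratory test is to be reported as an AE only if it meets SAE criteria or is the reason for stopping drug. Section 8.6, by contrast, gives withholding drug as an example of what makes a laboratory result clinically significant. The row followed may therefore decide whether an AE is recorded at all.
- **The pause criterion.** It counts attributed discontinuations, and a hold followed by a restart is not one.

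**Working it through.** The point is textual. The 20% trigger is a stated rule, not a derived figure, so there is no plan figure to reproduce.

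**Step 1: apply each row to a Grade 4 event judged not COVID-19-related.**

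| Event | Its own row | Blanket row | Conflict |
|---|---|---|---|
| Neutrophils, recovered to Grade 1 or baseline in 2 days | Restart | Discontinue | Express |
| Platelets, recovered to Grade 2 or better in 2 days | Restart | Discontinue | Express |
| Nausea, vomiting or diarrhea, not persistent | Condition not met, no action written | Discontinue | Implied |
| Hypertension, not persistent | Condition not met, no action written | Discontinue | Implied |
| Arrhythmia, not sustained and stable | Condition not met, no action written | Discontinue | Implied |
| Any other toxicity, not persistent | Row may exclude what the row before it covers | Discontinue | Not necessary |

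Of the 13 event rows, two conflict expressly with the blanket row and three by implication. The rest are not relied on.

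**Step 2: effect on one subject's exposure.** Suppose, as an illustration, that the event follows the sixth dose. Under hold and restart, missed doses are made up, so up to 20 × 100 mg = 2000 mg can be given. SAP Section 3.2.2 defines percentage of intended dose as 100 × d/2000, which gives 100%. Under discontinuation, d = 6 × 100 = 600 mg and the percentage is 100 × 600/2000 = 30%.

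**Step 3: effect on the pause criterion.** The smallest triggering count among n treated subjects is r, the smallest whole number with r/n ≥ 0.20.

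| n | r | r/n | (r − 1)/n |
|---|---|---|---|
| 10 | 2 | 20% | 10% |
| 11 | 3 | 27.3% | 18.2% |
| 15 | 3 | 20% | 13.3% |
| 20 | 4 | 20% | 15% |
| 25 | 5 | 20% | 16% |
| 30 | 6 | 20% | 16.7% |

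One reclassified event decides the pause only if the other attributed discontinuations number exactly r − 1. At n = 10, moving from 1 to 2 triggers it. At n = 11, the same move does not (2/11 = 18.2%).

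**Step 4: chance of triggering, under assumed rates.** The documents give no Grade 4 cytopenia rate for 10-day dosing. Table 5 in Protocol Section 6.6 shows Grade 3 or higher neutropenia in 14.2% and thrombocytopenia in 4.8%, but under chronic dosing in hematologic malignancy, and the protocol warns that this setting differs. The rates p below are therefore assumptions. The middle columns give P(X ≥ r) with X ~ Binomial(n, p) at a single look. The last column is from 40,000 simulated sequences checked after every subject from the 10th to the 30th, because the criterion applies at any time.

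| p | n = 10 | n = 15 | n = 30 | Ever, n = 10 to 30 |
|---|---|---|---|---|
| 5% | 0.086 | 0.036 | 0.003 | 0.095 |
| 8% | 0.188 | 0.113 | 0.029 | 0.225 |
| 10% | 0.264 | 0.184 | 0.073 | 0.328 |
| 15% | 0.456 | 0.396 | 0.289 | 0.590 |

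Reclassified events adding 3, 5 or 10 points to a 5% base move the trial from the first row to the second, third or fourth. Adding 5 points to a 10% base moves it from the third to the fourth.

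**The case against.** The best defense is that the blanket row sits under the Other heading, after the hematological, gastrointestinal/hepatic, cardiovascular and infection blocks. The cytopenia rows, with their 3-day recovery rules, would be pointless if the blanket row overrode them, so the specific row should govern. That is a sensible reading, but the protocol does not state it. The wording also points the other way: the blanket row begins with a bare *Any*, while the row directly below it says *Any other*.

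Sites can also use clinical judgment (Section 6.7), and Section 8 sends immediate safety concerns to the Medical Monitor to settle whether treatment continues. This gives a central route for resolving individual cases. It does not supply a rule of precedence.

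Three stronger readings are tempting, and the documents do not support them:

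- **A reader might count six conflicting rows.** Only two contain opposite written actions. The gastrointestinal, hypertension and arrhythmia rows never say to continue or restart, and the last row can be read as leaving out whatever the blanket row covers.
- **A reader might infer that the safety pause was generally unreliable.** The effect needs a count one below the threshold. The criterion leads to a pause and review, not termination, and the death and Grade 4 hemorrhage criteria are untouched. SAP Section 1.3 reports recruitment complete with 62 randomized, so no future pause is at stake.
- **A reader might want the trigger redefined as permanent discontinuations.** This adds little, because Section 4.4 already refers to discontinuation and Section 6.7 separates it from a hold.

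The analytic reach is also limited. Safety analyses are descriptive without p-values (SAP Section 4.4), and the main efficacy analysis keeps every subject in the randomized arm whatever treatment was received.

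**Conclusion.** The table is wrong as written. For a Grade 4 neutrophil or platelet decrease that is not COVID-19-related and recovers within 3 days, it gives two incompatible written instructions and no order between them. Three further rows are inconsistent with the blanket row by implication only.

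The main consequences are inconsistent treatment of a recognized safety event and a discontinuation count that may not mean the same thing at every site. The pause-trigger effect is secondary: it arose only at borderline counts while enrollment was open, and its probability rests on assumed event rates.

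The conclusion assumes that the event is judged unrelated to COVID-19 and that sites take the rows at face value. It takes no view on which clinical action is right.

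**What to change.** Reconcile the rows of the Section 6.7 table so that each Grade 4 event has one action, and state the precedence between the event-specific rows and the blanket Grade 4 row. Make the implied cases (gastrointestinal, hypertension, arrhythmia) explicit in the same edit. Table 4 in Section 6.5.4 should be checked against the result, since it gives dose reduction for intolerable Grade 3-4 events attributed to acalabrutinib in subjects on moderate CYP3A inhibitors. Which action applies is for the sponsor's clinical team.

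Because recruitment is complete, the study report should also show the action taken for each Grade 4 event in acalabrutinib-treated subjects, so that the discontinuation count can be interpreted. The AE listing in SAP Section 4.4.1 already carries grade and action taken, and Protocol Section 6.4 has interruptions and discontinuations recorded in the eCRF.

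The cost is one wording change, by amendment or clarification letter, with no new data or procedures.
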